5.2.2 Radiation Treatment

5.2.2.1 Dose Specifications

The prescribed radiotherapy dose will be 70 Gy in 2 Gy once-daily fraction size (total of 35 fractions). Radiotherapy should begin on a Monday, Tuesday or Wednesday. The daily dose of 2 Gy will be prescribed such that 95% of the PTV volume receives at least 95% of prescribed dose. The spinal cord dose may not exceed 45 Gy to any volume larger than 0.03 cc.

5.2.2.2 Technical Factors

Treatment Planning/Delivery: Megavoltage energy photon beam irradiation is required. IMRT treatment planning with simultaneous integrated boost (SIB) will be used, and treatment verification films must be taken daily (kv films or cone beam CT).

5.2.2.3 Localization, Simulation, and Immobilization

1. Patients must have an immobilization device (e.g., aquaplast mask extending to shoulders) made prior to treatment planning CT scan.
2. All patients will undergo CT simulation for treatment planning. The treatment planning CT scan may be completed with or without IV contrast. The treatment planning CT scan must be performed with the immobilization device and in the treatment position. Slice thickness should be 0.3 cm or less.

5.2.2.4 Target and Normal Tissue Volume Restrictions

1. Definition of Target Volumes

GTV70: This volume includes all gross tumor volume (primary tumor and nodal disease) based on clinical exam, PETCT scan and/or planning CT.

CTV70: This volume will receive 2 Gy per fraction. CTV70 will include the primary tumor plus a 1.0 cm circumferential margin added for microscopic spread. This volume may be decreased in size as appropriate around structures that represent barriers to anatomic spread of tumor, and up to 1.5 cm expansion may be added for suspicion on significant laryngeal movement with swallowing.

CTV56: This will include all other regions felt to be at risk for harboring microscopic cancer that do not meet the criteria for CTV70. For example, this would apply to bilateral necks irradiated electively. This volume will receive 1.6 Gy per fraction.

CTV63 **Optional:** This may be defined at the discretion of the treating radiation oncologist. This would include a region or regions felt to be at especially high risk for recurrence (e.g., first echelon nodal regions that are clinically negative). This area will be receiving a daily fraction size of 1.8 Gy.

Planning Target Volumes (PTVs): In general, the PTV should be pulled 3mm off of skin unless the skin is clinically involved with tumor.

PTV Expansion The CTV-to- PTV expansion is 3 mm as daily image guidance will be employed.

2. Definition of Normal Tissues/Organs at Risk (OARs)

Spinal Cord: The cord begins at the cranial-cervical junction (i.e., the top of the C1 vertebral body). Superior to this is brainstem and inferior to this is cord. The inferior border of the spinal cord is at approximately T3-4 (i.e., just below the lowest slice level that has PTV on it). The spinal cord shall be defined based on the treatment planning CT scan. In addition, however, a Planning Risk Volume (PRV) spinal cord shall be defined. The PRVcord = cord + 5 mm in each dimension.

Brainstem: The inferior most portion of the brainstem is at the cranial-cervical junction where it meets the spinal cord. For the purposes of this study, the superior most portion of the brainstem is approximately at the level of the top of the posterior clinoid. The brainstem shall be defined based on the treatment planning CT scan. In addition, however, a Planning Risk Volume (PRV) brainstem shall be defined. The PRVbrainstem = brainstem + 3 mm in each dimension.

Lips and Oral Cavity: These should be contoured as 2 separate structures as the goal is to keep the lip dose much lower than the oral cavity dose. The definition of lips is self-explanatory. The oral cavity will be defined as a composite structure consisting of the anterior $\frac{1}{2}$ to $\frac{2}{3}$ of the oral tongue/floor of mouth, buccal mucosa, and palate.

Parotid Glands: Parotid glands will be defined based on the treatment planning CT scan.

OARpharynx: This will be defined as the posterior pharyngeal wall plus adjacent constrictor muscles. This extends from the superior constrictor region (the inferior pterygoid plates level) to the cricopharyngeal inlet (posterior cricoid cartilage level) excluding the PTVs.

Cervical Esophagus: This will be defined as a tubular structure that starts at the bottom of OARpharynx and extends to the thoracic inlet, excluding the PTVs.

Glottic/Supraglottic Larynx (GSL): This will be defined as a “triangular prism shaped” volume that begins just inferior to the hyoid bone and extends to the cricoid cartilage inferiorly and extends from the anterior commissure to include the arytenoids. This includes the infrahyoid but not suprahyoid epiglottis.

Mandible: This includes the entire boney structure of the mandible from TMJ through the symphysis. It is recognized that for oral cavity cancers, this may overlap with CTVs and PTVs.

Unspecified Tissue Outside the Targets: This will be defined as tissue located between the skull base and thoracic inlet that is not included in either the target volumes or the normal tissues described above.

5.2.2.5 Treatment Planning and Delivery

1. Dose Prescription to PTVs

As described above, prescribed radiotherapy dose will be 70 Gy in 2 Gy once-daily fraction size. For inverse planning IMRT, the goal is for 95% of the PTV70 to receive 95% of 70 Gy with a minimum dose (cold spot) of no less than 63 Gy.

For IMRT prioritization, PTV70 will be the highest priority target structure. PTV63 and PTV56, if applicable, will be ranked in the IMRT planning as lower priority than PTV70 although higher priority than normal structures other than spinal cord and brain stem.

2. Dose Constraints to Normal Structures

Spinal Cord: The PRVcord should not exceed 45 Gy to any volume in excess of 0.03 cc (approximately 3 mm x 3 mm x 3 mm). The spinal cord PRV should not exceed 50 Gy to any volume in excess of 0.01 cc. In treatment planning, the spinal cord PRV should be given the highest priority.

Brainstem: The PRVbrainstem should not exceed 50 Gy to any volume in excess of 0.03 cc (approximately 3 mm x 3 mm x 3 mm). In treatment planning, the PRVbrainstem should be given less priority than the PRVcord but more priority than the other critical structures listed below.

Lips: Reduce the dose as much as possible unless lips involved with primary tumor. The mean dose should be < 20 Gy. The maximum dose will be < 30 Gy.

Oral Cavity: Reduce the dose as much as possible. The suggested mean dose should be < 30 Gy.

Parotid Glands: In most cases, it will be easier to spare one parotid than the other. The treatment planning goal will be for this individual parotid gland to receive a mean dose of < 26 Gy. Additional planning goals may include: 1) At least 50% of one parotid will receive < 30 Gy; and/or 2) At least 20 cc of parotid tissue (from the combination of both glands) will receive < 20 Gy.

OARpharynx: Reduce the dose as much as possible to uninvolved regions. Some recommended (but not mandatory) treatment goals include: 1) No more than 33% of the OARpharynx exceeds 50 Gy; 2) Mean dose < 45 Gy; 3) No more than 15% of the OARpharynx exceeds 60 Gy.

Cervical Esophagus: Reduce the dose as much as possible to uninvolved regions. Some recommended doses (but not mandatory) treatment goals include: 1) No more than 33% of the esophagus exceeds 50 Gy; 2) Mean dose < 45 Gy; 3) No more than 15% of the esophagus exceeds 60 Gy.

Mandible: Reduce the dose as much as possible; hot spots within the mandible should be avoided. It is recommended that maximum dose within the mandible be < 66 Gy. For tumors that were not clinically or pathologically involving the mandible, the CTV should be contoured off the mandible.

5.2.2.6 Compliance Criteria

Treatment breaks must be clearly indicated in the treatment record along with the reason(s) for the treatment break(s). Treatment breaks, if necessary, ideally should not exceed five treatment days at a time and ten treatment days total. Treatment breaks should be allowed only for resolution of severe acute toxicity and/or for intercurrent illness and not for social or logistical reasons.

5.2.2.7 Radiation Therapy Adverse Events

The descriptions and grading scales found in the revised NCI Common Terminology Criteria for Adverse Events (CTCAE), version 4.0 will be utilized for grading all adverse events. Placement of a feeding tube should be recorded as should use of a feeding tube during and after treatment (e.g., greater than or less than 50% of nutrition by tube). Other common radiation adverse events include: fatigue, weight loss, regional alopecia, xerostomia, hoarseness, transient ear discomfort, and skin erythema and desquamation within the treatment fields. Less common long-term treatment adverse events include: hypothyroidism, loss of hearing, chronic swallowing dysfunction requiring permanent feeding tube, and skin/soft tissue fibrosis. Much less common radiation adverse events include: mandibular osteoradionecrosis, and cervical myelopathy (< 1% with restriction of spinal cord dose to max dose of 45 Gy).

5.3 Trial Blinding/Masking

This is an open-label trial; therefore, the Sponsor, investigator and subject will know the treatment administered.

5.4 Randomization or Treatment Allocation

All patients enrolled in this study will receive the combination of All patients enrolled in this study will receive the combination of pembrolizumab, cisplatin and radiation.

5.5 Concomitant Medications/Vaccinations (allowed & prohibited)

Medications or vaccinations specifically prohibited in the exclusion criteria are not allowed during the ongoing trial. If there is a clinical indication for one of these or other medications or vaccinations specifically prohibited during the trial, discontinuation from trial therapy or vaccination may be required. The investigator should discuss any questions regarding this with the Merck Clinical team. The final decision on any supportive therapy or vaccination rests with the investigator and/or the subject's primary physician.

5.5.1 Acceptable Concomitant Medications

All treatments that the investigator considers necessary for a subject's welfare may be administered at the discretion of the investigator in keeping with the community standards of medical care. All concomitant medication will be recorded on the case report form (CRF) including all prescription, over-the-counter (OTC), herbal supplements, and IV medications and fluids. If changes occur during the trial period, documentation of drug dosage, frequency, route, and date may also be included on the CRF.

All concomitant medications received within 28 days before the first dose of trial treatment and 30 days after the last dose of trial treatment should be recorded. Concomitant medications administered after 30 days after the last dose of trial treatment should be recorded for SAEs and ECIs as defined in Section 7.2.

5.5.2 Prohibited Concomitant Medications

Subjects are prohibited from receiving the following therapies during the Screening and Treatment Phase (including retreatment for post-complete response relapse) of this trial:

- Antineoplastic systemic chemotherapy or biological therapy
- Immunotherapy not specified in this protocol
- Chemotherapy not specified in this protocol
- Investigational agents other than pembrolizumab
- Radiation therapy to any area other than specified in laryngeal carcinoma treatment protocol
- Live vaccines within 30 days prior to the first dose of trial treatment and while participating in the trial. Examples of live vaccines include, but are not limited to, the following: measles, mumps, rubella, varicella/zoster, yellow fever, rabies, BCG, and typhoid vaccine.
- Systemic glucocorticoids for any purpose other than to modulate symptoms from an event of clinical interest of suspected immunologic etiology. Premedication with steroids may be administered on Cycle 1 Day 1, if required by institutional standards. However, due to their immunosuppressive effect, steroids are encouraged to be discontinued within 72 hours. The use of physiologic doses of corticosteroids may be approved after consultation with the Sponsor.

Subjects who, in the assessment by the investigator, require the use of any of the aforementioned treatments for clinical management should be removed from the trial. Subjects may receive other medications that the investigator deems to be medically necessary.

The Exclusion Criteria describes other medications which are prohibited in this trial. There are no prohibited therapies during the Post-Treatment Follow-up Phase.

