5.6.2 Cisplatin Supportive Care Guidelines

- **Fluid and Electrolyte Imbalance**

Patients must be vigorously hydrated and diuresed before cisplatin administration as per institutional standard regimens.

- **Nausea and Vomiting**

High dose cisplatin is a highly emetogenic regimen with significant incidence of delayed nausea and vomiting. The following guidelines will be followed:

For acute nausea and vomiting, premedication should include a 5-HT₃ antagonist, such as granisetron 1 mg iv; ondansetron, up to 16 mg iv; or palonosetron, 0.25 mg iv; plus a corticosteroid, such as dexamethasone, up to 20 mg iv.

Breakthrough nausea and vomiting should be managed at the discretion of the medical oncologist or radiation oncologist.

Delayed nausea and vomiting (greater than 24 hours after chemotherapy administration) may be managed by the addition of aprepitant concurrently or with metoclopramide and dexamethasone.

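### Section 5.5.2 has no steroid exemption for the antiemetic premedication that Section 5.6.2 calls for at the day 22 and day 43 cisplatin doses

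*Combined protocol and SAP*

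**What the plan says.** Section 5.5.2 lists therapies that are not allowed in the Screening and Treatment Phase. One entry is "Systemic glucocorticoids for any purpose other than to modulate symptoms from an event of clinical interest of suspected immunologic etiology". Two further allowances follow in the same bullet: "Premedication with steroids may be administered on Cycle 1 Day 1, if required by institutional standards", and "The use of physiologic doses of corticosteroids may be approved after consultation with the Sponsor". The section then says that subjects who, in the investigator's assessment, "require the use of any of the aforementioned treatments for clinical management should be removed from the trial".

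Section 5.6.2 covers supportive care for cisplatin. It states: "High dose cisplatin is a highly emetogenic regimen with significant incidence of delayed nausea and vomiting". It then says "The following guidelines will be followed", and that premedication for acute nausea and vomiting should combine a 5-HT3 antagonist "plus a corticosteroid, such as dexamethasone, up to 20 mg iv". No dose number or cycle is mentioned. For delayed symptoms, more than 24 hours after chemotherapy, dexamethasone with metoclopramide is one option and aprepitant the other.

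Section 5.5, the parent of 5.5.2, says that a clinical need for a prohibited drug may lead to discontinuation from trial therapy. It adds: "The final decision on any supportive therapy or vaccination rests with the investigator", and/or the subject's primary physician.

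**The concern.** The two sections give different instructions for the same visits. An investigator who follows 5.6.2 at the second or third cisplatin dose gives a drug that 5.5.2 prohibits. One who follows 5.5.2 leaves out part of the antiemetic regimen that the protocol itself sets for a highly emetogenic drug.

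Three things are at stake: patient care, consistent conduct, and a clean deviation log. Section 5.5.2 justifies its restriction by the immunosuppressive effect of steroids, and the flow chart schedules pembrolizumab at the same day 1, 22 and 43 visits as cisplatin. Whether up to 20 mg of dexamethasone may accompany those doses is therefore a design decision. As written, it falls to each investigator, and steroid exposure or antiemetic care may differ between patients for no planned reason.

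**Working it through.** No power, alpha or event figure is involved, so this is a cross-check of the text plus one count.

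**Step 1. When cisplatin is given.** Table 2 (Section 5.2) allows a maximum of 3 doses, every 3 weeks. Section 5.2.1.4 and the flow chart (Section 6.1) place them on days 1, 22 and 43. The flow chart labels these C1 D1, C1 D22 and C1 D43. Table 2 instead speaks of day 1 of each 3-week cycle. Under either labelling, days 22 and 43 are not Cycle 1 Day 1.

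**Step 2. Test each exception in 5.5.2 against the later doses.**

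| Exception in 5.5.2 | Does it cover antiemetic steroid on days 22 and 43? |
|---|---|
| Symptoms of a suspected immune-related event of clinical interest | No. Antiemetic prophylaxis is a different purpose. |
| Premedication on Cycle 1 Day 1, where institutional standards require it | No. It is tied to one visit. |
| Physiologic doses after consulting the Sponsor | No. 5.6.2 does not present the dexamethasone as physiologic replacement, nor make it depend on consultation. |

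**Step 3. Count.** Planned doses 3, doses covered at most 1, so 3 − 1 = 2 planned doses per patient have no exemption. Day 1 itself is covered only if institutional standards require the premedication.

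**Step 4. Look for text that lifts the ban.** Section 5.5.1 generally allows treatments the investigator considers necessary for the subject's welfare. The closing allowance in 5.5.2 for other medically necessary medications comes directly after the removal rule for the listed therapies, so it most naturally means drugs not on the list. Section 5.5 gives the investigator and/or primary physician the final decision. None of these mentions antiemetic steroids, and the protocol states no order of precedence between 5.5.2 and 5.6.2.

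**Step 5. Delayed emesis.** Dexamethasone is only one of the options in 5.6.2, so an investigator can satisfy both sections by choosing aprepitant. This is a gap worth closing, not a strict conflict.

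**Step 6. Reach into the analysis.** Section 8 defines no per-protocol set and no exclusion for prohibited medication. The Kaplan-Meier estimate and z-test for 18-month LFS are not altered by this wording.

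**The case against.** The strongest reply is that 5.5.2 was never meant to reach drugs the protocol itself specifies. Its first bullet bars systemic antineoplastic chemotherapy and biological therapy with no carve-out. Read literally, that would bar cisplatin and pembrolizumab. On this view 5.5.2 governs only therapy outside the regimen, and 5.6.2, as the more specific text on cisplatin, prevails. That is probably the intent and how most investigators would act. It does not settle the matter, because the steroid bullet itself deals with premedication and allows it at one visit. If protocol premedication were outside the ban, that allowance would be hard to explain.

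A second reply stands in part. Both provisions say *should*: removal in 5.5.2 and the corticosteroid in 5.6.2. Section 5.5 treats discontinuation as possible, not automatic, and refers questions to the drug supplier's clinical team. A reader might infer that the investigator is forced to breach one section, depart from the other, or remove the patient. The documents do not support that: giving the steroid under the final-decision clause in 5.5 is an available route. What remains is that the route rests on a general clause set against a specific prohibition.

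A reader might also multiply the two uncovered doses by the 47 patients and treat the product as expected deviations or removals. That is not supported either. Section 5.2.1.3 allows cisplatin to be stopped and delayed doses to be omitted, so a patient may receive only the first dose and never reach a conflicting visit.

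**Conclusion.** The conflict holds at 2 of the 3 planned cisplatin doses, days 22 and 43. Severity is minor. The conclusion rests on reading the steroid bullet as applying to cisplatin premedication, which its own Cycle 1 Day 1 allowance supports, and on the planned schedule; the number of affected doses a given patient actually receives can be 0, 1 or 2.

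The number of patients removed cannot be derived from the documents and may be zero. It would be tempting to infer that removals would bias the primary endpoint or shrink the evaluable sample. The documents do not support this: nothing in Section 8 excludes such patients, and Section 5.8 provides disease-status follow-up for subjects who discontinue for reasons other than progression.

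**What to change.** Add one sentence to 5.5.2, for example: Corticosteroids given as antiemetics under Section 5.6.2 with each cisplatin dose (days 1, 22 and 43) are permitted. If the sponsor keeps dexamethasone as an option for delayed emesis, the sentence should also name that short course. If the sponsor would rather limit steroids around pembrolizumab, 5.6.2 should be changed to say so; either way the two sections would then agree.

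The cost is a one-sentence wording amendment. Sample size, visits and analysis stay as they are.

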2.1.2 Phase II expansion

After the first 6 patients have been assessed for DLTs upon completion of cycle 1 of treatment, and the appropriate Cisplatin dose and Pembrolizumab dosing determined

for phase II expansion, an additional 41 patients with locally advanced larynx squamous cell carcinoma will be enrolled in this phase I/II study. The entire cohort will be used to assess the safety and efficacy outcomes of interest. Safety stopping rules will be applied in the event of excessive toxicity leading to inability of patients to receive at least 2 doses of cisplatin and complete radiation therapy. If radiation treatment breaks are required, greater than a 10 day radiation treatment break in 6 or more patients will also initiate early stop for safety evaluation.

Patients will be evaluated 14 weeks after completion of radiation (14 ± 2 week after completion of radiation) with radiographic imaging to assess response to treatment. All imaging will be assessed using Response Evaluation Criteria in Solid Tumors (RECIST) 1.1 Adverse events will be monitored throughout the trial and graded in severity according to the guidelines outlined in the NCI Common Terminology Criteria for Adverse Events (CTCAE) version 4.0.

After the end of treatment, each patient will be followed for a minimum of 30 days for adverse event monitoring (serious adverse events will be collected for up to 90 days after the end of treatment). Subjects will have post-treatment follow-up for laryngectomy event and survival status for two years.

Participation in this trial will be dependent upon supplying tumor tissue from a formalin-fixed specimen. Newly obtained formalin-fixed specimens are strongly encouraged 14-20 days after first dose of Pembrolizumab prior to initiation of cisplatin and radiation unless clinically deemed unsafe by the treating physician. The specimen will be evaluated for expression status of PD-L1.

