5.8 Subject Withdrawal/Discontinuation Criteria

Subjects may withdraw consent at any time for any reason or be dropped from the trial at the discretion of the investigator should any untoward effect occur. In addition, a subject may be withdrawn by the investigator or the Sponsor if enrollment into the trial is inappropriate, the trial plan is violated, or for administrative and/or other safety reasons. Specific details regarding discontinuation or withdrawal are provided in Section 7.1.4 – Other Procedures.

A subject must be discontinued from the trial for any of the following reasons:

- The subject or legal representative (such as a parent or legal guardian) withdraws consent.
- Confirmed radiographic disease progression
Note: For unconfirmed radiographic disease progression, please see Section 5.2.2
- Unacceptable adverse experiences as described in Section 5.2.1.2
- Intercurrent illness that prevents further administration of treatment
- Investigator's decision to withdraw the subject
- The subject has a confirmed positive serum pregnancy test
- Noncompliance with trial treatment or procedure requirements

- The subject is lost to follow-up
- Administrative reasons

The End of Treatment and Follow-up visit procedures are listed in Section 6 (Protocol Flow Chart) and Section 7.1.5 (Visit Requirements). After the end of treatment, each subject will be followed for 30 days for adverse event monitoring (serious adverse events will be collected for 90 days after the end of treatment as described in Section 7.2.3.1). Subjects who discontinue for reasons other than progressive disease will have post-treatment follow-up for disease status until disease progression, initiating a non-study cancer treatment, withdrawing consent or becoming lost to follow-up. After documented disease progression each subject will be followed by telephone for overall survival until death, withdrawal of consent, or the end of the study, whichever occurs first.

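### Section 5.5.2 removes patients who need a prohibited treatment from the trial, in conflict with 5.5 and the two-year laryngectomy follow-up in 2.1.2, and the plan does not say how they enter the LFS analysis

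*Combined protocol and SAP*

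**What the plan says.** **Consequence of needing a prohibited treatment.** Section 5.5.2 lists treatments that subjects are "prohibited from receiving the following therapies during the Screening and Treatment Phase": other systemic anticancer therapy, other immunotherapy, investigational agents, radiation elsewhere, live vaccines, and systemic glucocorticoids outside narrow exceptions. Those who, in the investigator's assessment, "require the use of any of the aforementioned treatments for clinical management should be removed from the trial". For the same situation, section 5.5 says that "discontinuation from trial therapy or vaccination may be required".

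**Follow-up and analysis set.** Section 2.1.2 says: "Subjects will have post-treatment follow-up for laryngectomy event and survival status for two years". It also says: "The entire cohort will be used to assess the safety and efficacy outcomes of interest".

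**Follow-up after leaving treatment.** Section 5.8 does not name prohibited medication among its mandatory reasons for discontinuation (it does list investigator decision and noncompliance). It adds: "Subjects who discontinue for reasons other than progressive disease will have post-treatment follow-up for disease status until disease progression". That follow-up also ends when non-study cancer treatment starts. Section 7.1.1.5.3 then moves the patient to survival follow-up, which 7.1.5.4.1 and the flow chart describe as a telephone contact every 12 weeks for survival status.

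**Analysis.** Section 8.2 estimates LFS by Kaplan-Meier and compares the 18-month value with 70% by a z-test. It gives no rule for patients removed from the trial.

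**Duration.** The vaccine item covers "Live vaccines within 30 days prior to the first dose of trial treatment and while participating in the trial", yet the section ends: "There are no prohibited therapies during the Post-Treatment Follow-up Phase".

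**The concern.** The two instructions differ in force (should against may) and in scope (the trial against trial therapy). The difference in scope matters more. Stopping a drug leaves the patient's LFS outcome observable, whereas leaving the trial may not.

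Kaplan-Meier treats a censored patient as having the same later risk as those still followed. A patient who needs other anticancer therapy during chemoradiation may well be at higher risk of laryngectomy or death. Censoring such patients would raise the 18-month estimate. This is a single-arm trial of 47 patients judged against a fixed 70%, so no control arm would share the error and a few patients can matter.

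**Working it through.** **1. The plan's own sample size.** Inputs from 8.1: 70% against 85% at 18 months, one-sided 10%, 80% power, 18 months of accrual, 6 months of further follow-up. I assumed exponential LFS and uniform accrual. The Greenwood term is g(p) = ∫ from 0 to 18 of λ / [S(t)G(t)] dt, with λ = −ln(p)/18, S(t) = exp(−λt), and G(t) = 1 up to 6 months, then (24 − t)/18.

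- g(0.70) = 0.635 and g(0.85) = 0.257.
- On the log(−log) scale, s = √g / |ln p|, so s0 = 2.234 and s1 = 3.117; the difference to detect is 0.786.
- n = [(1.2816 × 2.234 + 0.8416 × 3.117) / 0.786]² = 48.7, so 49. Power at 47 is 79.1%.

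This is within two patients of the stated 47. Nothing below alters these inputs.

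**2. Which removed patients keep endpoint follow-up?**

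| Reading | Deaths | Laryngectomies |
|---|---|---|
| 5.5.2 taken literally | not followed | not followed |
| With 5.8 and 7.1.5.4, no new anti-cancer therapy | followed | observable at 12-weekly exams |
| With 5.8, 7.1.1.5.3 and 7.1.5.4.1, new anti-cancer therapy | followed by telephone | promised in 2.1.2, but no procedure collects them |

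The last row is the gap that remains on the more generous reading. It concerns one of the two components of the composite endpoint.

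**3. Size if removed patients are censored.** Let f be the share removed and r their true 18-month LFS, with overall true LFS of 70%. If removal comes early and removed patients are censored there, Kaplan-Meier tends to the LFS of those who remain, (0.70 − f·r)/(1 − f). The documents give neither f nor r, so both are assumptions shown over a range.

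| f | r = 70% | r = 50% | r = 35% |
|---|---|---|---|
| 5% | 70.0% | 71.1% | 71.8% |
| 10% | 70.0% | 72.2% | 73.9% |
| 20% | 70.0% | 75.0% | 78.75% |

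Example: f = 10%, r = 50% gives (0.70 − 0.05)/0.90 = 0.722. Ten per cent of 47 is about five patients.

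**4. Effect on the test.** A simulation of the untransformed Kaplan-Meier z-test at N = 47 (8,000 replicates, true LFS 70%, removal at 1.5 months, accrual and follow-up as in 8.1) gave these rejection rates:

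| Case | Rejection rate |
|---|---|
| No removal | 14.4% |
| f = 5%, r = 50% / 35% | 17.4% / 19.4% |
| f = 10%, r = 70% / 50% / 35% | 14.8% / 21.8% / 27.8% |
| f = 10%, r = 50% / 35%, patients still followed | 14.8% / 13.8% |

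The baseline is about 14%, not the nominal 10%, because of the small-sample behaviour of the test. That is a separate matter, and the effect of removal should be measured from 14%. With follow-up kept, the excess disappears.

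**5. The glucocorticoid item.** Section 5.5.2 bars systemic glucocorticoids except for immune-related events, premedication on Cycle 1 Day 1, and physiologic doses approved after consultation with the Sponsor. Section 5.6.2 says cisplatin premedication should include a corticosteroid and allows dexamethasone for delayed nausea. The flow chart gives cisplatin on days 1, 22 and 43. Read literally, routine antiemetic care on the later days would meet the removal condition.

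**The case against.** A reader might infer that patients doing badly do leave the LFS estimate and that the result is therefore inflated. The documents do not support this.

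- Section 5.8 uses discontinuation from the trial for its own listed reasons and then describes follow-up of those very patients. In this protocol, leaving the trial need not end follow-up.
- Section 2.1.2 uses the entire cohort, and no section says removed patients are censored. Censoring is one possible reading of a silent analysis section.
- The prohibition covers screening and about 10 weeks of treatment (up to 3 weeks of lead-in plus 7 of radiation). Response imaging comes 14 ± 2 weeks after radiation, so new therapy prompted by that imaging falls where nothing is prohibited. Laryngectomy is not on the list.
- Several triggers say little about prognosis. A live vaccine does not mark a failing patient, and steroids given with cisplatin would catch nearly everyone.
- With 10% removed at 50% LFS, the bias is 2.2 points. The standard error of the Kaplan-Meier estimate at 70% with 47 patients is about 8 points (0.70 × √(0.635/47) = 0.081).

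All of this stands, and it reduces the point from a demonstrated bias to a possible one. It does not remove the conflict between 5.5.2, 5.5 and 2.1.2, the missing rule in 8.2, or the gap in laryngectomy data after new anti-cancer therapy.

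**Conclusion.** The point holds as a contradiction in the text with a conditional effect on the primary endpoint. Upward bias needs three things together: some patients are removed, they are censored or their laryngectomies go unrecorded, and they fare worse than the rest. With average prognosis the bias is zero. With 10% removed and LFS of 50% or 35% among them, it is 2.2 or 3.9 points, and simulated false rejection rises from about 14% to about 22% or 28%. These figures assume that both events and deaths are lost at removal. Where deaths are still captured by telephone, the effect would be smaller.

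The steroid conflict is separate and concrete: 5.5.2 and 5.6.2 cannot both be followed as written. The live-vaccine duration wording has no bearing on LFS and is only a minor inconsistency. The change is worth making because it is cheap and protects the primary endpoint.

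**What to change.** - **5.5.2:** separate any decision about study treatment from trial participation. State that treated patients stay in follow-up for laryngectomy and survival for two years unless they withdraw consent.
- **5.5 and 5.5.2:** reconcile the stated consequence for study treatment. Which consequence applies is for the investigators to decide.
- **5.5.2 and 5.6.2:** reconcile the glucocorticoid restriction with the cisplatin premedication and delayed-nausea provisions.
- **7.1.5.4.1 and the flow chart:** add laryngectomy status and date to the existing 12-weekly telephone contacts, and align the wording in 5.8.
- **8.2:** state that all treated patients are in the LFS analysis and are not censored at a prohibited treatment or at discontinuation of study treatment. Add a sensitivity analysis counting patients lost after removal as events.
- **Minor:** reconcile the two statements in 5.5.2 on how long live vaccines are barred.

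The cost is an amendment to wording and one added question in calls already scheduled. There are no new visits, and the sample size stays at 47.
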